9.5. Vital Signs

Values at each scheduled visit, change, and percentage change from baseline for vital signs, including systolic blood pressure, diastolic blood pressure, pulse, temperature, and respiratory rate will be summarized descriptively.

Normal ranges for vital sign values are defined in [Table 6](#). The abnormal values for participants exhibiting vital sign abnormalities will be listed along with their assigned treatment group. Alert vital signs are defined as an absolute value outside the defined normal range and percentage change greater than 25%. Note that the definition of alert vital signs does not apply for body

temperature. The abnormal values for participants exhibiting alert vital sign abnormalities will be listed.

Table 6: Normal Ranges for Vital Sign Values

Parameter	High Threshold	Low Threshold
Systolic blood pressure	≤ 155 mmHg	≥ 85 mmHg
Diastolic blood pressure	≤ 100 mmHg	≥ 40 mmHg
Pulse	≤ 100 bpm	≥ 45 bpm
Temperature	$\leq 38^{\circ}\text{C}$	$\geq 35.5^{\circ}\text{C}$
Respiratory rate	≤ 24 breaths/min	≥ 8 breaths/min

9.6. Electrocardiograms

Twelve-lead ECGs including PR, QT, QRS, QTcB, and QTcF intervals will be obtained for each participant during the study. Baseline will be determined as the last nonmissing ECG measurements taken on or before the first administration of study drug.

Normal ranges for ECG values are defined in [Table 7](#). ECG values will also be considered abnormal if the absolute percentage change from baseline is more than 25%. Participant exhibiting ECG abnormalities will be listed with study visit and assigned treatment group. Abnormal values for participant with alert ECG values, defined as both the absolute value and the percentage change from baseline being outside normal ranges, will be identified and listed. Outliers of QT, QTcB, and QTcF values, defined as absolute values > 450 ms, > 500 ms, or change from baseline > 30 ms, will be summarized.

Table 7: Normal Ranges for Electrocardiogram Intervals

Parameter	High Threshold	Low Threshold
PR	≤ 220 ms	≥ 75 ms
QT	≤ 500 ms	≥ 300 ms
QRS	≤ 120 ms	≥ 50 ms
QTcF, QTcB	≤ 460 ms	≥ 295 ms

QTcB = Bazett's correction; QTcF = Fridericia's correction.

In addition to ECG, echocardiogram may also be conducted, and data collected will be summarized and listed as appropriate.

9.7. Cytopenias Ongoing by Day 30

All the cytopenias \geq Grade 3 by Day 30 will be summarized. The laboratory tests on neutrophils, hemoglobin, and platelets will be included.

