3. OBJECTIVES AND ENDPOINTS

Table 7 presents the objectives and endpoints for Part 1 and Part 2, supporting selection of optimal dosing/schedule of itacitinib for subsequent trials.

Table 7: Objectives and Endpoints

Objectives	Endpoints
Primary	
To evaluate the efficacy of itacitinib as a preventative treatment for CRS associated with IEC therapy.	Efficacy, as determined by the proportion of participants who develop \geq Grade 2 CRS by Day 14, using ASBMT CRS Consensus Grading.
Secondary	
To evaluate the proportion of participants with ICANS regardless of CRS, after IEC therapy.	Incidence and severity of ICANS, as determined by the proportion of participants with ICANS by Day 28, after IEC therapy using the ICANS Consensus Grading.
To evaluate the onset and episode of ICANS using the ICANS Consensus Grading, regardless of CRS, by Day 28.	Time to onset and duration of ICANS using the ICANS Consensus Grading, regardless of CRS, by Day 28.
To evaluate the duration of all grades of CRS, by Day 28.	Time to onset and duration of all grades of CRS by Day 28 using ASBMT CRS Consensus Grading.
To evaluate the proportion of participants who develop any grade of CRS within 48 hours after IEC therapy.	Proportion of participants with any grade of CRS at 48 hours, after IEC therapy using ASBMT CRS Consensus Grading.
To evaluate the proportion of participants who develop \geq Grade 2 CRS by Day 28 of administration after first IEC therapy.	Proportion of participants with \geq Grade 2 CRS by Day 28, after first IEC therapy.
To characterize the safety of itacitinib, before and after IEC therapy, excluding CRS and ICANS.	Safety of itacitinib assessed by the incidence of all AEs except CRS and ICANS, by collecting laboratory data, performing physical examinations, and collecting vital signs beginning at Day -3 and through the duration of safety follow-up.
	\geq Grade 3 Cytopenias ongoing by Day 30.
To evaluate the number of and length of hospital admissions for CRS and ICANS.	Number of hospital admissions and duration of stay for participants with CRS and/or ICANS by EOS.
To assess intervention for CRS and ICANS.	Proportion of participants who were treated with tocolizumab for CRS.
	Proportion of participants requiring more than 1 dose of dexamethasone (or equivalent) for ICANS.

Table 7: Objectives and Endpoints (Continued)

Objectives and Endpoints	Definition

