5.2. Exclusion Criteria

Participants are excluded from the study if any of the following criteria apply:

1. Evidence of active uncontrolled/untreated infection (viral, bacterial, fungal, opportunistic) of any origin.
2. Evidence of active HBV or HCV infection as defined in Section [8.3.5.2](#).
3. Known human immunodeficiency virus.
4. Active acute or chronic GVHD requiring systemic therapy.
5. Concurrent use of chronic systemic steroids or immunosuppressant medications.
6. Known hypersensitivity or severe reaction to itacitinib, similar compounds, or excipients of itacitinib.
7. Any unresolved toxicity \geq Grade 2 (except stable Grade 2 peripheral neuropathy or alopecia) from previous anticancer therapy.
8. Participants with a known history or prior diagnosis of immunologic or inflammatory/autoimmune disease affecting the CNS, and unrelated to their disease under study or previous treatment.
9. Clinically significant or uncontrolled cardiac disease, including unstable angina, acute myocardial infarction within 6 months from Day –3 of itacitinib administration, New York Heart Association Class III or IV congestive heart failure, and circulatory collapse requiring vasopressor or inotropic support. Participants with arrhythmias that are not stable on a medical management program within 2 weeks of induction Day –3 are also excluded.
10. Central nervous system status:
 - a. Acute lymphoblastic leukemia participants with the following CNS status are eligible only in the absence of neurologic symptoms suggestive of CNS leukemia, such as cranial nerve palsy:
 - CNS1, defined as absence of blasts in CSF on cytospin preparation, regardless of the number of WBCs.
 - CNS2, defined as presence of $< 0.5 \times 10^9/L$ WBCs in CSF and cytospin positive for blasts, or $> 5/\mu L$ WBCs, but negative by Steinherz/Bleyer algorithm:
 - CNS2a: $< 1.0 \times 10^9/L$ RBCs; $< 0.5 \times 10^9/L$ WBCs and cytospin positive for blasts.
 - CNS2b: $\geq 1.0 \times 10^9/L$ RBCs; $< 0.5 \times 10^9/L$ WBCs and cytospin positive for blasts.
 - CNS2c: $\geq 1.0 \times 10^9/L$ RBCs; $\geq 0.5 \times 10^9/L$ WBCs and cytospin positive for blast, but negative by Steinherz/Bleyer algorithm.

b. Diffuse large B-cell lymphoma participants: Participants must have no signs or symptoms of CNS disease or detectable evidence of CNS disease; participants who have been previously treated for CNS disease but have no evidence of disease at screening are eligible.

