11. Participants who are currently breastfeeding.

12. Receipt of a prior investigational study agent within 4 weeks before screening visit.

Note: Participants who have received anti-CD19 IEC therapy on a study where cell infusion occurred greater than 4 weeks before the screening visit are NOT excluded.

13. Any condition that would, in the investigator's judgment, interfere with full participation in the study, including administration of itacitinib and attending required study visits (if outpatient); pose a significant risk to the participant; or interfere with interpretation of study data.

14. Inability of the participant to swallow and retain oral medication.

15. Participants with laboratory values at screening defined in [Table 8](#).

Table 8: Exclusionary Laboratory Values

Laboratory Parameter		Exclusion Criterion
Hematology		
a	Platelets	$\leq 10 \times 10^9/L$
b	Hemoglobin	$\leq 8 \text{ g/dL}$
Hepatic		
e	ALT	$\geq 2.5 \times \text{ULN}$ for age, $> 5 \times \text{ULN}$ in the presence of liver metastases
f	AST	$\geq 2.5 \times \text{ULN}$ for age, $> 5 \times \text{ULN}$ in the presence of liver metastases
g	Total bilirubin	$> 1.5 \times \text{ULN}$ or $> 3 \times \text{ULN}$ in the presence of documented Gilbert's syndrome (unconjugated hyperbilirubinemia)
Renal		
h	Creatinine clearance	
Participants ≥ 18 years of age: $\leq 50 \text{ mL/minute}$ based on Cockcroft-Gault formula.
 
Participants < 18 years of age: GFR < 15 based on revised Schwartz formula 2009.
 
The cutoffs for mild, moderate, and severe renal insufficiency based on Cockcroft-Gault are 60-90 mL/min, 30-59 mL/min, and 0-29 mL/min, respectively.
 
Note: Creatinine clearance necessitates a 24-hour urine sample before the blood draw to calculate. An estimated value is acceptable.

Cardiopulmonary		
i	Cardiac LVEF	$\leq 40\%$ confirmed by ECHO/multigated analysis
j	Adequate pulmonary function	$\geq \text{Grade 2 dyspnea}$ and $\geq \text{Grade 2 hypoxia}$

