3. STUDY DESIGN

3.1. Overall Study Design

This is a 2-part Phase 2 study designed to assess the safety and efficacy of oral administration of itacitinib for the prevention of CRS in male or female participants planning to receive IEC therapy for any approved hematologic indication.

- In Part 1, approximately 62 participants older than 12 years will be administered itacitinib 200 mg QD (open label). Based on the Protocol-defined analysis in Protocol Amendment 2, 10 participants with ALL will be included.
- In Part 2, approximately 46 evaluable participants older than 18 years will be randomized to receive either itacitinib 200 mg BID or placebo.

This study includes a 14-day screening period after apheresis. Apheresis will be per institutional standard of care. Conditioning chemotherapy will be administered at the discretion of the investigator.

Participants will be administered study drug beginning at Day -3 to Day -1 before IEC infusion. Immune effector cell therapy will be administered on Day 0 along with study drug. Participants will continue to receive study drug through Day 26 to complete a 30-day study treatment period.

During the treatment period, Protocol-defined assessments will be conducted on Day -3, Day -1, Day 0 (IEC infusion day), Day 1, Day 3, Day 5, Day 7, Day 14, Day 21, and Day 28. Restaging of hematologic disease will be conducted per institutional guidelines. Completers are defined as participants who complete 30 days of itacitinib administration (Day -3 to Day 26). An EOT assessment will be conducted at Day 28 ± 2 days. Additional post-therapy follow-up visits will be conducted 30 days after the last dose of itacitinib and 90 and 180 days after IEC infusion. End of study is met at Day 180.

Safety will be monitored beginning at screening and will continue through to a 30-day post-treatment safety follow-up visit.

Hematologic disease assessments should be conducted as indicated in the SoA. The date of the assessment as well as the results should be recorded in the eCRF.

A planned interim analysis for CRS futility will be conducted when 24 participants in Part 1 are treated with an approved IEC therapy and complete the Day 28 (EOT) visit. The study may be stopped for futility at the interim analysis if the conditional power based on interim results is lower than 20%, which is equivalent to more than 17 out of 24 participants experiencing \geq Grade 2 CRS by Day 14.

See [Figure 1](#) and [Figure 2](#) for the study design.

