4.1.5. Baseline Value

Baseline is the last nonmissing assessment obtained before the first administration of study drug for safety analysis. For efficacy endpoints related to IEC therapy, the last nonmissing assessment prior to IEC therapy may be taken as baseline depending on the specific analysis to be conducted.

When scheduled assessments and unscheduled assessments occur on the same day and time of the assessment or time of first dose is not available, use the following convention to determine baseline:

- If both a scheduled and an unscheduled visit are available on the day of the first dose and the time is missing, use the scheduled assessment as baseline.
- If all scheduled assessments are missing on the day of the first dose and an unscheduled assessment is available, use the unscheduled assessment as baseline.

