3.3 Laboratory (update per data collection)		
3.3.1.1	Summary of Laboratory Hematology Values	Safety
3.3.1.2	Summary of Laboratory Chemistry Values	Safety
3.3.1.3	Summary of Laboratory Coagulation Values	Safety
3.3.1.4	Summary of Laboratory Urinalysis Values	Safety
3.3.1.5	Summary of Laboratory Lipid Values	Safety
3.3.2.1	Shift Summary of Hematology Laboratory Values to the Worst Abnormal Value	Safety
3.3.2.2	Shift Summary of Chemistry Laboratory Values to the Worst Abnormal Value	Safety
3.3.2.3	Shift Summary of Coagulation Laboratory Values to the Worst Abnormal Value	Safety
3.3.3.1	Shift Summary of Hematology Laboratory Values in CTC Grade to the Worst Abnormal Value	Safety
3.3.3.2	Shift Summary of Chemistry Laboratory Values in CTC Grade to the Worst Abnormal Value	Safety
3.3.3.3	Shift Summary of Coagulation Laboratory Values in CTC Grade to the Worst Abnormal Value	Safety
3.3.3.4	Treatment-Emergent Worsening of Laboratory Abnormalities - Hematology	Safety
3.3.3.5	Treatment-Emergent Worsening of Laboratory Abnormalities - Chemistry	Safety
3.3.3.6	Treatment-Emergent Worsening of Laboratory Abnormalities - Coagulation	Safety
3.3.6	Summary of Liver Chemistry	Safety
3.3.7	Summary of Grade 3 or Higher Cytopenias Rate	EAS

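### The Day 30 cytopenia endpoint ignores the pre-dose grade, so a participant who enters at Grade 3 or higher and does not change is counted like a new case

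*SAP*

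**What the plan says.** The protocol (Section 3, Table 7) lists "\geq Grade 3 Cytopenias ongoing by Day 30" as a secondary safety endpoint. SAP 9.7 keeps the word *ongoing* in its heading but not in its rule: "All the cytopenias \geq Grade 3 by Day 30 will be summarized". It adds that "The laboratory tests on neutrophils, hemoglobin, and platelets will be included". The planned output is Table 3.3.7 in SAP Appendix A, titled "Summary of Grade 3 or Higher Cytopenias Rate", with no mention of Day 30 or of baseline.

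The SAP does have a safety baseline. Section 4.1.5 states: "Baseline is the last nonmissing assessment obtained before the first administration of study drug for safety analysis". Section 9.7 does not refer to it.

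Three passages bear on who can enter with a low count:

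- Protocol 5.2, Table 8 excludes platelets at or below 10 × 10^9/L and hemoglobin at or below 8 g/dL. No neutrophil row is visible; the row letters go from b to e.
- Protocol 5.2, Exclusion 7 bars "Any unresolved toxicity \geq Grade 2 (except stable Grade 2 peripheral neuropathy or alopecia) from previous anticancer therapy".
- SAP 3.1 says: "Conditioning chemotherapy will be administered at the discretion of the investigator". Neither document times conditioning relative to Day -3.

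Protocol 10.4.3 presents the safety endpoints by the two dose groups and placebo, and uses this to confirm the choice of dose.

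**The concern.** The endpoint is there to characterize the safety of itacitinib, and Protocol 2.4 names a potential for myelosuppression. A rate that mixes severe cytopenia present before the first dose with severe cytopenia that arose later answers that question poorly. The platelet limit of 10 × 10^9/L lies well below any plausible Grade 3 threshold, so the eligibility table itself foresees participants who already meet the event definition on entry.

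The more exposed comparison is across the two parts. The 200 mg QD group is Part 1, which includes ALL and mantle cell lymphoma (SAP 3.1 and 5.2). The BID and placebo groups are Part 2, which is Yescarta-treated lymphoma only. Nothing balances entry counts between them, yet the safety tables across the three groups feed into dose selection.

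**Working it through.** **Plan figure.** There is none to reproduce. The documents give no expected cytopenia rate, no power for this endpoint, no entry distribution of counts and no CTCAE cut-offs. All inputs below are assumptions unless a source is named.

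**1. Who can enter at Grade 3 or higher.** Table 8 alone admits a platelet count of, say, 15 × 10^9/L. Exclusion 7, read at face value, removes that participant if the low count is an unresolved toxicity of previous anticancer therapy. Entry then remains open for cytopenia due to the disease, or due to conditioning if that is not counted as previous therapy. The two passages are hard to read together and need to be reconciled.

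**2. Share below a platelet cut-off at entry, before Exclusion 7.** Take platelets as lognormal with median m and log-scale SD s, truncated above 10 (Table 8). With F(x) = Φ[(ln x − ln m)/s], the share below cut-off c is [F(c) − F(10)] / [1 − F(10)]. The assumed Grade 3 cut-off is 50 × 10^9/L, varied down to 25.

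| m, s | F(10) | F(25) | F(50) | Share < 25 | Share < 50 |
|---|---|---|---|---|---|
| 150, 0.6 | < 0.0001 | 0.0014 | 0.0335 | 0.1% | 3.4% |
| 120, 0.7 | 0.0002 | 0.0125 | 0.1055 | 1.2% | 10.5% |
| 80, 0.9 | 0.0104 | 0.0981 | 0.3008 | 8.9% | 29.3% |

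**3. Effect on the reported rate.** Let b be the share who enter at Grade 3 or higher and are still there, and q the rate of new cases among the rest. The rate as written is b + (1 − b)q. With q = 20%:

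- b = 5%: 0.05 + 0.95 × 0.20 = 24%
- b = 10%: 28%
- b = 20%: 36%
- b = 30%: 44%

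A rate limited to participants below Grade 3 at baseline is 20% in every row. In Part 1 (n = 62), 62b is about 3, 6, 12 and 19 participants.

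**4. Part 2 (23 per arm).** Randomization makes b equal on average, so a true difference d among those without baseline cytopenia appears as (1 − b)d. With d = 15 points this is 13.5, 12.0 and 10.5 points at b = 10%, 20% and 30%. The SD of the chance difference in b between arms is √[2b(1 − b)/23] = 8.8, 11.8 and 13.5 points. If entry cases are binomial in each arm, the probability that the arms differ by two or more such participants is 17% at b = 3%, 45% at 10% and 58% at 20%. For three or more it is 3%, 21% and 35%.

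**5. Part 1 against Part 2.** Here b need not be equal. If b were 20% in the QD group and 10% in a Part 2 group, with the same q = 20%, the reported rates would be 36% and 28%. That is an 8-point gap with no difference in new cytopenia.

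**6. Whether another table already gives this.** SAP 9.4.2 and Appendix A plan hematology shift tables from baseline to the worst postbaseline grade, and Table 3.3.3.4 covers treatment-emergent worsening. Both use baseline, but neither is tied to Day 30. They do not show which of the events in Table 3.3.7 were present before dosing.

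**The case against.** The case against has real weight, and parts of it stand.

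- *Exclusion 7 closes much of the gap.* It does so for treatment-caused cytopenia. A reader might infer that anyone with platelets of 15 × 10^9/L is simply eligible; the documents do not support that without qualification. The shares in step 2 ignore this filter and are therefore upper readings of each scenario.
- *No neutrophil limit.* A reader might infer that eligibility sets none. Table 8 shows none, but rows c and d are absent directly after the hematology rows, so this cannot be confirmed from the available text. The platelet argument does not need it.
- *Hemoglobin.* It is tempting to extend the point to hemoglobin because the entry limit may sit on the Grade 3 boundary. Values at or below 8 g/dL are excluded at screening, so on that assumed boundary no one enters at Grade 3. Later variation around 8 g/dL is post-entry noise, which a baseline split would not remove.
- *Bias in Part 2.* A reader might infer a biased comparison with placebo. Allocation is 1:1 at random, so only dilution and noise remain.
- *Part 1 is uncontrolled anyway.* True: a baseline flag does not turn a single-arm rate into a drug effect. It only removes one known source of unrelated events.
- *Status is a legitimate endpoint.* Counting everyone who is severely cytopenic at a time point is a valid description, which is why the all-participant rate should stay.
- *Baseline is reported elsewhere, and Part 1 is shown by IEC product* (SAP 5.2), so a Yescarta column exists. This helps, but that column is still not randomized against Part 2 and still has no pre-dose split at Day 30.

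A conditioning nadir that falls after the last pre-dose value would still be counted as new under the proposed split.

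**Conclusion.** The point holds in a limited form. SAP 9.7 counts every Grade 3 or higher cytopenia by Day 30 without reference to the pre-dose grade, and eligibility does not rule out entry at that grade, at least for platelets. Within Part 2 the result is dilution and noise without average bias. Across the Part 1 QD group and the Part 2 groups it can confound a comparison that Protocol 10.4.3 uses for dose selection.

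The size is unknown. The range of about 0.1% to 29% below the cut-off at entry rests on assumed platelet distributions, on assumed Grade 3 cut-offs of 25 to 50 × 10^9/L, and on leaving Exclusion 7 aside. No test or decision threshold depends on this endpoint, so this is a low-cost improvement rather than a threat to the primary result.

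**What to change.** In SAP 9.7 and Table 3.3.7, for each of the three lineages:

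1. Report the Grade 3 or higher rate among participants whose last pre-dose value (SAP 4.1.5) was below Grade 3. For Part 2, give the difference from placebo with its 95% CI.
2. Show participants already at Grade 3 or higher at baseline on a separate line.
3. Keep the all-participant rate as a second line.

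Bring the SAP sentence into line with the protocol endpoint by counting cytopenias ongoing at Day 30, not any that occurred by then. The nearest scheduled visit is Day 28 ± 2 days, so the text should name the assessment used. Separately, the sponsor should reconcile Exclusion 7 with the platelet limit in Table 8 and state whether a neutrophil criterion exists.

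The cost is SAP wording and one baseline flag per lineage. Pre-dose hematology is already required (Protocol Table 3 and 8.3.5). The downside is a slightly smaller denominator for each lineage.

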10. INTERIM ANALYSES

For Part 1, an interim analysis is planned after approximately 24 participants are dosed with IEC therapy and complete the Day 28 (EOT) visit. The results from the interim analysis will be reviewed by the DSMB. The primary intent of this analysis is to minimize unnecessary exposure to itacitinib in the event of futility of treating CRS. The study may be stopped for futility at the interim analysis if the conditional power based on interim results is lower than 20%, which is equivalent to more than 17 out of 24 participants experiencing \geq Grade 2 CRS by Day 14. More than 24 participants may be available in EAS at the time of interim analysis, and the stopping boundary will be re-evaluated at the time of the analysis. [REDACTED]

[REDACTED] Enrollment will continue while the analysis is being conducted.

No interim analysis is planned for Part 2.

